Appendix 3.6 36-item Short Form

The RAND Corporation SF-36 Survey Instrument was developed at RAND as part of the Medical Outcomes Study. An example is shown below:

Your Health and Well-Being

This survey asks for your views about your health. This information will help keep track of how you feel and how well you are able to do your usual activities.
Thank you for completing this survey!

For each of the following questions, please tick the one box that best describes your answer.

1. In general, would you say your health is:

[figure not shown]
Excellent	Very good	Good	Fair	Poor
 1	 2	 3	 4	 5

2. Compared to one year ago, how would you rate your health in general now?

Much better now than one year ago	Somewhat better now than one year ago	About the same as one year ago	Somewhat worse now than one year ago	Much worse now than one year ago
 1	 2	 3	 4	 5

SF-36v2® Health Survey © 1992, 2002, 2009 Medical Outcomes Trust and QualityMetric Incorporated. All rights reserved.
SF-36® is a registered trademark of Medical Outcomes Trust.
(SF-36v2® Health Survey Standard, United Kingdom (English))

3. The following questions are about activities you might do during a typical day. Does your health now limit you in these activities? If so, how much?

- a Vigorous activities, such as running, lifting heavy objects, participating in strenuous sports 1 2 3
- b Moderate activities, such as moving a table, pushing a vacuum cleaner, bowling, or playing golf 1 2 3
- c Lifting or carrying groceries 1 2 3
- d Climbing several flights of stairs 1 2 3
- e Climbing one flight of stairs 1 2 3
- f Bending, kneeling, or stooping 1 2 3
- g Walking more than a mile 1 2 3
- h Walking several hundred yards 1 2 3
- i Walking one hundred yards 1 2 3
- j Bathing or dressing yourself 1 2 3

SF-36v2® Health Survey © 1992, 2002, 2009 Medical Outcomes Trust and QualityMetric Incorporated. All rights reserved.
 SF-36® is a registered trademark of Medical Outcomes Trust.
 (SF-36v2® Health Survey Standard, United Kingdom (English))

4. During the past 4 weeks, how much of the time have you had any of the following problems with your work or other regular daily activities as a result of your physical health?

	All of the time	Most of the time	Some of the time	A little of the time	None of the time
	▼	▼	▼	▼	▼

[figure not shown]
- a Cut down on the amount of time you spent on work or other activities 1..... 2..... 3..... 4..... 5
- b Accomplished less than you would like 1..... 2..... 3..... 4..... 5
- c Were limited in the kind of work or other activities 1..... 2..... 3..... 4..... 5
- d Had difficulty performing the work or other activities (for example, it took extra effort) 1..... 2..... 3..... 4..... 5

5. During the past 4 weeks, how much of the time have you had any of the following problems with your work or other regular daily activities as a result of any emotional problems (such as feeling depressed or anxious)?

[figure not shown]
	All of the time	Most of the time	Some of the time	A little of the time	None of the time
	▼	▼	▼	▼	▼

- a Cut down on the amount of time you spent on work or other activities 1..... 2..... 3..... 4..... 5
- b Accomplished less than you would like 1..... 2..... 3..... 4..... 5
- c Did work or other activities less carefully than usual 1..... 2..... 3..... 4..... 5

[figure not shown]
6. During the past 4 weeks, to what extent has your physical health or emotional problems interfered with your normal social activities with family, friends, neighbours, or groups?

7. How much bodily pain have you had during the past 4 weeks?

8. During the past 4 weeks, how much did pain interfere with your normal work (including both work outside the home and housework)?

9. These questions are about how you feel and how things have been with you during the past 4 weeks. For each question, please give the one answer that comes closest to the way you have been feeling. How much of the time during the past 4 weeks...

	All of the time	Most of the time	Some of the time	A little of the time	None of the time
a Did you feel full of life?	 1	 2	 3	 4	 5
b Have you been very nervous?	 1	 2	 3	 4	 5
c Have you felt so down in the dumps that nothing could cheer you up?	 1	 2	 3	 4	 5
d Have you felt calm and peaceful?	 1	 2	 3	 4	 5
e Did you have a lot of energy?	 1	 2	 3	 4	 5
f Have you felt downhearted and low?	 1	 2	 3	 4	 5
g Did you feel worn out?	 1	 2	 3	 4	 5
h Have you been happy?	 1	 2	 3	 4	 5
i Did you feel tired?	 1	 2	 3	 4	 5

10. During the past 4 weeks, how much of the time has your physical health or emotional problems interfered with your social activities (like visiting with friends, relatives, etc.)?

	All of the time	Most of the time	Some of the time	A little of the time	None of the time
	 1	 2	 3	 4	 5

SF-36v2® Health Survey © 1992, 2002, 2009 Medical Outcomes Trust and QualityMetric Incorporated. All rights reserved.
 SF-36® is a registered trademark of Medical Outcomes Trust.
 (SF-36v2® Health Survey Standard, United Kingdom (English))

11. How TRUE or FALSE is each of the following statements for you?

Definitely true	Mostly true	Don't know	Mostly false	Definitely false
▼	▼	▼	▼	▼

- a I seem to get ill more easily than other people 1 2 3 4 5
- b I am as healthy as anybody I know 1 2 3 4 5
- c I expect my health to get worse 1 2 3 4 5
- d My health is excellent 1 2 3 4 5

Thank you for completing these questions!

Study Code: GWND18064
EudraCT Number: 2018-003370-27
Clinical Protocol 4.1, 07Jul2020 (duplicate synopsis removed)

Appendix 3.7 Tanner Staging

Tanner Staging⁷² is to be completed for all patients aged 7 to less than 18 years of age⁷⁰ at the time of signing the informed consent/assent form, or earlier if clinically indicated by onset of menarche or other signs of precocious puberty).

Female Development & Pubic Hair

Please check the box next to the most appropriate stage; in the event that qualifying characteristics are not within the same stage, defer to the lesser stage as the overall Tanner Score.

Tanner Stage 1 (Prepubertal, typically 10 years and younger)

- No glandular tissue; areola follows the skin contours of the chest.
- No pubic hair at all.

Tanner Stage 2 (10–11.5 years)

- Breast bud forms, with small area of surrounding glandular tissue; areola begins to widen.
- Small amount of long, downy hair with slight pigmentation on the labia majora.

Tanner Stage 3 (11.5–13 years)

- Breast begins to become more elevated, and extends beyond the borders of the areola, which continues to widen but remains in contour with surrounding breast.
- Hair becomes more coarse and curly and begins to extend laterally.

Tanner Stage 4 (13–15 years)

- Increased breast size and elevation; areola and papilla form a secondary mound projecting from the contour of the surrounding breast.
- Adult-like hair quality, extending across pubis but sparing medial thighs.

Tanner Stage 5 (15+ years)

- Breast reaches final adult size; areola returns to contour of the surrounding breast, with a projecting central papilla.
- Hair extends to medial surface of the thighs.

Study Code: GWND18064
EudraCT Number: 2018-003370-27
Clinical Protocol 4.1, 07Jul2020 (duplicate synopsis removed)

Male Genital Development & Pubic Hair

Please check the box next to the most appropriate stage.

Tanner Stage 1 (Prepubertal, typically 9 years and younger)

- Testicular volume less than 1.5 mL; small penis of 3 cm or less.
- No pubic hair at all.

Tanner Stage 2 (9–11 years)

- Testicular volume between 1.6 and 6 mL; skin on scrotum thins, reddens, and enlarges; penis length unchanged.
- Small amount of long, downy hair with slight pigmentation at the base of the penis and scrotum.

Tanner Stage 3 (11–12.5 years)

- Testicular volume between 6 and 12 mL; scrotum enlarges further; penis begins to lengthen to about 6 cm.
- Hair becomes more coarse and curly and begins to extend laterally.

Tanner Stage 4 (12.5–14 years)

- Testicular volume between 12 and 20 mL; scrotum enlarges further and darkens; penis increases in length to 10 cm and circumference.
- Adult-like hair quality, extending across pubis but sparing medial thighs.

Tanner Stage 5 (14+ years)

- Testicular volume greater than 20 mL; adult scrotum and penis of 15 cm in length.
- Hair extends to medial surface of the thighs.

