9.2.18 Tanner Staging

The pubic hair (both sexes), genital (males only) and breast (females only) growth of all adolescent patients (i.e., \geq 7 years of age⁷⁰ at the time of signing the informed consent form, or earlier if clinically indicated by onset of menarche or other signs of precocious puberty) will be assessed using Tanner Staging (see [Appendix 3.7](#))⁷². The assessment can either be performed by examination during the study visit or the appropriate Tanner Stage can be indicated by the caregiver, with reference to the chart provided.

Once a patient reaches a score of V (i.e., 5) the assessment need not be performed again.

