### **9.3.5 Growth and Development**

IGF-1 levels will be analyzed as part of the clinical laboratory testing. IGF-1 levels will be summarized on a continuous scale, including change from baseline, by treatment group.

Change from baseline to the end of treatment visit for IGF-1 levels will also be plotted against the Tanner Stages, weight, and height recorded at baseline.

The pubic hair growth (both sexes), genital (males only) and breast (females only) development of all adolescent patients (i.e.,  $\geq 7$  years of age at the time of signing the informed consent form, or earlier if clinically indicated by onset of menarche or other signs of precocious puberty) will be assessed using Tanner Staging. The assessment can either be performed by examination during the study visit or the appropriate Tanner Stage can be indicated by the caregiver, with reference to the chart provided.

Patients will be examined at Visit 1 (screening) and Visit 9 (end of treatment). Once a patient reaches a score of V (i.e., 5) the examination need not be performed again.

Tanner Stages will be summarized on a categorical scale, by treatment group. Shift table will be created to display shifts from baseline.

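### The female Tanner form keeps only the lower of the breast and pubic-hair stages, so some one-component advances cannot appear in the planned shift table

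*Protocol*

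**What the plan says.** Growth and development, including Tanner staging, is a listed safety endpoint in both documents (Protocol 4.1.2; SAP 2.2.2).

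Protocol 9.2.18 names more than one feature to be assessed: "The pubic hair (both sexes), genital (males only) and breast (females only) growth of all adolescent patients". It allows two methods: "The assessment can either be performed by examination during the study visit or the appropriate Tanner Stage can be indicated by the caregiver". SAP 9.3.5 repeats both statements. Staging takes place at Visits 1 and 9.

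The female form in Appendix 3.7 lists a breast description and a pubic-hair description under each stage, asks for one stage, and adds: "in the event that qualifying characteristics are not within the same stage, defer to the lesser stage as the overall Tanner Score". The male form says only "Please check the box next to the most appropriate stage" and has no rule for the case where the two features disagree.

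The visit sections (Protocol 9.1.1.1 and 9.1.1.7) and 9.2.18 speak of a Tanner stage or score in the singular. The planned analysis in SAP 9.3.5 is: "Tanner Stages will be summarized on a categorical scale, by treatment group. Shift table will be created to display shifts from baseline". Neither document says that the two features are stored or tabulated separately.

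**The concern.** The rater judges two features, but the female form keeps one number, and the rule for disagreement discards the more advanced of the two. A girl who moves from breast 1 / hair 1 at screening to breast 3 / hair 1 at end of treatment is recorded as stage 1 at both visits. In the shift table she is indistinguishable from a girl in whom nothing changed.

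The loss runs in one direction. The rule can hide or shrink an advance but cannot create one, so the Tanner table leans towards no change. It applies in every arm. If treatment did accelerate one feature, the rule would dilute any difference between arms as well as the count within each arm.

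The female form governs most of the trial: the disease section of the protocol (3.1) describes the condition as only rarely seen in boys. Equal starting stages should also be common. Routine staging begins at age 7, and the female form describes stage 1 as typical up to age 10, so by the form's own guide many of the younger staged girls would start at stage 1 on both features.

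**Working it through.** The plan gives no figure on this point, so there is nothing of its own to reproduce. The check is on the logic of the rule.

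**Inputs.** Breast stage *b* and pubic-hair stage *h*, each 1 to 5 (Appendix 3.7). Recorded female stage = min(*b*, *h*) (Appendix 3.7). Shift = recorded stage at Visit 9 compared with Visit 1 (SAP 9.3.5).

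**Step 1: count the one-stage advances in a single component.** There are 5 × 5 = 25 pairs. Breast can advance from 4 stages at each of 5 hair stages, giving 20; the same holds for hair. The total is 40. An advance is hidden if min(*b*, *h*) is the same before and after.

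| Starting position | Possible one-stage advances | Hidden | Shown |
|---|---|---|---|
| Equal stages, either component advances | 8 | 8 | 0 |
| Unequal, the component ahead advances | 12 | 12 | 0 |
| Unequal, the component behind advances | 20 | 0 | 20 |
| Total | 40 | 20 | 20 |

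Examples: 1/1 to 2/1 gives 1 to 1 (hidden). Breast 3 / hair 2 to 4/2 gives 2 to 2 (hidden). Breast 2 / hair 3 to 3/3 gives 2 to 3 (shown).

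**Step 2: advances of any size.** The pattern is the same: 20 of 20 hidden from equal stages, 20 of 20 hidden when the component ahead advances, and 0 of 60 hidden when the component behind advances. A visible advance can still be understated: 1/2 to 4/2 is recorded as 1 to 2.

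**Step 3: what this could mean in patients.** The documents give neither starting stages nor the rate or correlation of advance, so this step is an illustration on assumed values. Suppose a girl starts at equal stages, each component advances over 24 weeks with probability *p*, and the two advances have correlation *r*. Then:

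- both advance (recorded shift): *p*² + *r p*(1 − *p*)
- at least one advances: 2*p* − P(both)
- hidden: the difference, 2*p*(1 − *p*)(1 − *r*)

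| *p* | *r* = 0: recorded / any | *r* = 0.8: recorded / any | *r* = 1: recorded / any |
|---|---|---|---|
| 0.1 | 1% / 19% | 8.2% / 11.8% | 10% / 10% |
| 0.2 | 4% / 36% | 16.8% / 23.2% | 20% / 20% |

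For *p* = 0.1 and *r* = 0.8: 0.01 + 0.8 × 0.09 = 0.082, and 0.2 − 0.082 = 0.118. The hidden share runs from large under independence to none under perfect correlation. Both features belong to the same puberty, so independence is the extreme case and should not be quoted as the expected size.

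**The case against.** **The form is only an example.** Appendix 3 says that its forms illustrate content and that the electronic format will differ. The electronic form and the table shells are separate documents, and SAP 9.3.5 does not name the variable it tabulates. So a shift table of the overall score is the natural reading, not a stated fact. This stands as a caveat. But a scoring rule is content rather than format, and no table shell can recover a component stage that was not recorded.

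**Other data could pick up the change.** Adverse events, physical examinations at Visits 5, 7 and 9, menstruation, height, weight and IGF-1 are all collected. That limits the safety consequence but does not repair the Tanner table.

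**The trial was discontinued and the SAP is descriptive only.** This is true, and it lowers the stakes. The shift table is still planned, and a descriptive table is read at face value.

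Four stronger readings are tempting, and the documents do not support them:

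- *Any advance in one component is hidden, or the table moves only if both advance.* Not so: every advance of the component that is behind shows. Both having to advance is true only from equal stages.
- *The hidden changes are an early sign of abnormal puberty.* Neither document says this. Precocious puberty appears only as a reason to stage before age 7.
- *Recorded shifts reflect a change of rater.* The method may differ between visits because nothing requires it to be the same, but nothing shows that it does differ.
- *The rule favours one arm.* It is the same in all blinded arms.

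**Conclusion.** The point holds in a limited form. Under the lesser-stage rule, an advance in one component from equal stages, or in the component already ahead, cannot appear in a shift table of the overall female stage; an advance in the component behind can. In terms of possible one-stage transitions that is 20 hidden out of 40, including all 8 from equal stages. The number of patients affected cannot be derived from the documents.

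This rests on two assumptions: that the data-collection form follows the Appendix 3.7 rule, and that SAP 9.3.5 tabulates that single score. It is a weakness in how a safety endpoint is measured, not evidence that a safety signal was missed. It is worth correcting because the correction is cheap and the loss runs only towards no change.

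**What to change.** - **Protocol Appendix 3.7 and 9.2.18:** drop the lesser-stage rule. Record breast (or genital) stage and pubic-hair stage as two fields for both sexes, which also settles disagreement on the male form. Record for each whether it came from examination or from the caregiver's chart. Say whether the existing exemption from repeat staging after stage V applies to each component.
- **SAP 9.3.5:** name the variables, and give one shift table per component by treatment group.
- **Visits already completed:** if component stages were captured, use them. If only the overall score exists, an edit to the SAP cannot restore them. State there, and in a footnote to the table, that for girls the shift table shows the lower of the two stages and can miss an advance in one component.

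The cost is one extra stage field, a method tick, and one extra table. The rater already judges both features, so no new procedure or visit is needed. Where data collection is closed, the cost is one sentence in the SAP and one footnote.

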Appendix 3.8 Hospital Services Use Questionnaire

An example of the Hospital Services Use Questionnaire (based on the Health Service Use Questionnaire⁷³) is shown below:

Baseline

- Has your child used any **hospital in-patient** services in the last 12 months? (prior to starting treatment with the Study Medicine)? *[in-patient services include: Intensive Care Unit [ICU] and other hospital department wards]*

Yes/No

- Has your child used any **other specialist medical services** in the last 6 months? *[other hospital services include: Emergency department, other outpatient departments (any hospital clinic e.g., neurology, cardiology, gastroenterology, etc.), Urgent care.*

Yes/No

For each in-patient hospital admission in the last 12 months, please record the following:

Reason for stay	Ward	Total Number of inpatient days

 Health issue Accident related to child's condition (due to motor disability or behaviour) Accident unrelated to child's condition 	
 Intensive Care Unit (ICU) Other department / ward (non-ICU) 	

Please complete additional in-patient hospital admission forms for each admission that occurred in the last 12 months

Please record any use of other **specialist medical services** by your child over the last 6 months.

Services used	Number of attendances due to health issues	Number of attendances due to accidents related to child's condition (due to motor disability or behaviour)	Number of attendances due to accidents unrelated to child's condition
Emergency department			
Other outpatient specialist services department			

SPONSOR: GW RESEARCH LIMITED

Study Code: GWND18064
EudraCT Number: 2018-003370-27
Clinical Protocol 4.1, 07Jul2020 (duplicate synopsis removed)

(any hospital clinic e.g., neurology, cardiology, gastroenterology, etc.)			
Urgent Care			

Since last visit

1. Has your child used any **hospital in-patient** services since the last study visit? (prior to starting treatment with the Study Medicine)? *[in-patient services include: Intensive Care Unit [ICU] and other hospital department wards]*
Yes/No
2. Has your child used any **other specialist medical services** since the last study visit? *[other hospital services include: Emergency department, other outpatient departments (any hospital clinic e.g., neurology, cardiology, gastroenterology, etc.), Urgent care.]*
Yes/No

For each in-patient hospital admission since the last study visit, please record the following:

Reason for stay	Ward	Total Number of inpatient days
1. Health issue 2. Accident related to child's condition (due to motor disability or behaviour) 3. Accident unrelated to child's condition	1. Intensive Care Unit (ICU) 2. Other department / ward (non-ICU)	

Please complete additional in-patient hospital admission forms for each admission that occurred since the last study visit

Please record any use of other **specialist medical services** by your child since the last study visit.

Services used	Number of attendances due to health issues	Number of attendances due to accidents related to child's condition (due to motor disability or behaviour)	Number of attendances due to accidents unrelated to child's condition
Emergency department			
Other outpatient specialist services department (any hospital clinic e.g., neurology, cardiology, gastroenterology, etc.)			
Urgent Care			

Appendix 3.9 Suicidality Assessment

An example of the suicidality assessment is shown below:

- *Has the child expressed any wish to be dead?*
- *Has the child made any suicide attempts?*
- *Has the child harmed themselves in any way or shown any non-suicidal self-injurious behavior?*

